stratification. However, in the event that considerable variability does occur, patients will be stratified based on their pre-treatment CAPS total score and randomly assigned to condition within strata. The project statistician will be responsible for randomization of participants.

**Therapists: Background and assignment to condition:** In this proposed study, we elected to nest therapists within condition for **three** reasons. **First**, we have no reason to suspect that study therapists will have particular enthusiasm for either treatment, as they have not been involved in the development of this project. **Second**, because these two treatments share some common features (e.g., facilitation of a supportive environment, provision of information about PTSD), we are concerned that therapists might become confused if counterbalanced. **Third**, therapists will be equivalent with respect to skill level, experience with veterans, and other factors that potentially could be confounds (e.g., sex ).

Each treatment group at each site will be conducted by two therapists. Therapists will be doctoral level psychologists, who have a wealth of experience treating veterans with PTSD. The therapists also will have extensive experience delivering CBT and delivering group treatment. Therapists in the two treatment conditions will be matched for experience and demographic characteristics (e.g., race, sex). These procedures will ensure that any observed treatment condition differences are not due to therapist effects.

**Treatment Procedures:** The two treatments to be used in this study will be delivered using structured treatment manuals (as described in Section D.2; see Appendix). Each therapist team will meet with either [name] or [name] once per week for supervision. Each treatment session will be recorded to permit close supervision and assessment of treatment fidelity and integrity. [name] will serve as supervisor for GCBT and [name] will serve as supervisor for *SGP*.

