**Is this RCT adequately statistically powered?** In the study design, several factors were involved in determination of sample size. **First**, we drew estimated effect sizes from the **two** pilot studies on GCBT and from a recent meta-analysis (Bradley et al., 2005). Within the MVA pilot study, which contrasted GCBT with a minimal contact comparison condition, effect sizes for PTSD measures ranged from .83 to 1.04 (Hedges's unbiased  $g$ , Hedges, 1981). Within our Vietnam veteran pilot data, the pre-post treatment effect size for the PCL-M was  $d = 1.43$ . Consulting the larger literature, Bradley et al. (2005) computed average effect sizes (Cohen's  $d$ ) of .84 for contrasts between CBT versus supportive therapy conditions and 1.01 for contrasts between ET + cognitive therapy versus supportive therapy conditions. However, in RCTs involving veterans, effect sizes tend to be smaller, owing to the chronicity and severity of combat-related PTSD in this population. In computation of sample size for this trial, we have selected a relatively low value of  $d$  (.50); review of available studies (including our own pilot data) suggests effect sizes ranging from 0.84 to 1.43. Recognizing that effect sizes for contrasts between CBT and supportive psychotherapy tend to average  $d = .84$  (Bradley et al., 2005), that data from samples with chronic PTSD tend to have smaller effects, relative to less severe samples, and that effect sizes drawn from relatively small samples can be unstable, we took a conservative stance in estimating the effect size for the GCBT versus SGP contrast to arrive at  $d = .50$ . **Second**, because treatment within both conditions of this RCT will occur in groups, the analytic plan must account for the cluster effect owing to the correlation of outcomes within groups (expressed as  $\rho$ , the intraclass correlation coefficient). There is one clustered variable in this design (individuals within groups) which will be adjusted for in determining sample size. Following guidelines provided by Hsieh (1988) and Diggle et al. (2002), we used an inflation factor that was driven by the  $\rho$  values from the MVA-related PTSD pilot data. In particular, the  $\rho$  estimate of 0.11 is a conservative assumption, based on the largest value obtained in the pilot MVA study. In the pilot MVA study ([name] et al., 2009), the  $\rho$  for the CAPS was 0.07, the  $\rho$  for the BDI-II was 0.03, and for the BAI, the  $\rho$  was 0.08. Within the Collaborative 420 study (Schnurr

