
et al., 2003), the  $\rho$  for the CAPS was 0.05. Thus, use of  $\rho = 0.11$  in our power calculations is a conservative assumption. Larger values of the  $\rho$  can occur when the outcome measures (among patients) have a concrete connection to one another. In studies of physician behavior within a clinic, the  $\rho$  values are larger when the physician directly contributes to the assessment of the patient outcome measures. For example, Stedman et al. (2008) analyzed two such studies, one study of patients within selected clinics who were followed to determine if their clinic physician did or did not provide osteoporosis management, and a second study of patients within clinics to determine if physician education induced physicians to improve the quality of osteoporosis management. In each study the  $\rho = 0.12$ . The outcome measure for the patient was the level of disease management delivered by the physician, an outcome directly determined by the physician. In contrast, for our proposed study, the person who assesses patient outcomes should have little or no effect on the values of the patient measure outcome. In our study, the  $\rho$  captures a subtler effect, namely, potential assessor bias, a much smaller effect than the effect of physician practice patterns. With a proposed group size of 7, a maximum  $\rho$  of 0.11, and  $d = 0.50$ , we estimated a total  $n$  of 196, using  $p < .05$ . Although only two of 14 outcome variables in the pilot study exceeded  $\rho > .10$  (see [name] et al., 2009), we felt it was preferable to be conservative regarding  $\rho$  levels in our power computations. **Third**, in computation of sample size, we relied on .80 power level, as is customary in power calculations for RCTs. Using these parameters, the total desired  $n$  will be 196 ( $n = 98$  per condition); each treatment group will begin with 7 men. Thus, based on previous studies on Group CBT, as well as current data regarding ICC in the context of clinical trials, we have been appropriately conservative in our power calculations.

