extent of dependency (i.e., clustering) by calculation of intraclass correlations (ICCs) using variance estimates from unconditional cell means models of key outcome variables (cluster = treatment group). Our proposed  $N$  of 196 will be clustered into 14 treatment groups per condition. Assuming non-zero ICCs, a multilevel approach will be incorporated into the latent growth framework in order to obtain correct standard errors, test statistics, and confidence intervals. In the traditional multilevel modeling, the design would be construed as a three-level model; i.e., repeated observations (Level 1) nested under individuals (Level 2), individuals nested under treatment groups (Level 3). However, because the first two levels are combined in the multivariate framework of latent growth modeling, this design can be characterized as a two-level model (i.e., latent growth factors are nested under treatment groups) where time-invariant covariates (i.e., dummy codes for treatment condition) are included to account for the within-group and between-group variability in initial status (pre-treatment) and symptom change (improvement over active treatment and follow-up). In the latent growth model portion of the models, the intercept will be centered on pre-treatment (i.e., first slope loading will be fixed to 0.0). Because there is no substantive interest in the form of the growth trajectory, intermittent time points (i.e., slope factor loadings) will be freely estimated and the final timepoint of interest (e.g., post-treatment) will have a corresponding factor loading fixed to 1.0. Accordingly, the mean and variance of the slope will convey the fixed (average) and random effects (individual differences) of change for the given time interval of interest. The Level 2 variables of treatment condition (single dummy code using *SGP* as reference group) will be included as predictors to account for individual differences in treatment response and variability in outcome across treatment groups. To examine pre-treatment differences between treatment conditions, the intercept (centered on pre-treatment) will be regressed onto the treatment covariates (i.e., significant paths are indicative of differences in pre-treatment levels as a function of treatment condition). Any pre-treatment differences will be accommodated into the interpretation of findings and in the parameterization of the models (e.g., regression of the slope onto the intercept, as well as covariates such as treatment condition). The dependent variable for this analysis is the CAPS total score. Additionally, PCL will be examined, using the same analytic approach, in order to examine respondent effects (interviewer-rated versus self-report).

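### Therapists work in one arm only, so the plan cannot rule out therapist effects; if pairs lead several groups, its group-only model understates the standard error

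*Combined protocol and SAP*

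**What the plan says.** In D.3, under the therapists' background and assignment, the investigators write "we elected to nest therapists within condition" and give three reasons: no expected allegiance to either treatment, a risk of confusion if therapists delivered both, and equivalence of skill and experience. "Each treatment group at each site will be conducted by two therapists". Therapists are matched across conditions on experience and demographic characteristics such as race and sex. The paragraph ends: "These procedures will ensure that any observed treatment condition differences are not due to therapist effects".

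The power section (on whether the RCT is adequately powered) recognises a single level of clustering: "There is one clustered variable in this design (individuals within groups) which will be adjusted for in determining sample size". It then describes the intraclass correlation as a subtle effect, "namely, potential assessor bias, a much smaller effect than the effect of physician practice patterns".

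D.7.a sets out three levels: occasions, individuals and treatment groups, with 14 groups per condition. No analysis in D.7 has a therapist or therapist-pair term.

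**The concern.** Two separate things are at issue.

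The first is the assurance. Matching on a few observed characteristics can reduce differences between the two sets of therapists. It cannot exclude them, and no random assignment of therapists to condition is described. Skill, alliance and other unmatched qualities stay inseparable from condition. The supervisor also differs by condition. This holds however many therapists there are.

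The second is the standard error. If one pair leads several groups, those groups share a source of variation that a group-level model treats as independent. The confidence interval is then too narrow and the test rejects too often. A positive result could rest partly on a few therapists, while the protocol says that this cannot happen.

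**Working it through.** **The plan's own figure.** With d = 0.50, two-sided 5% and 80% power, the individual-level requirement is 2 × (1.960 + 0.842)² / 0.50² = 62.8, so 63 per arm. The design effect is 1 + (7 − 1) × 0.11 = 1.66, and 63 × 1.66 = 104.6, so 105 per arm or 210 in total, against the stated 196. That gap is a separate matter and is not used here. What matters is that the inflation has one term, for the group, and none for therapists.

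**Is reuse implied?**
- 196 / 7 = 28 groups. With two therapists each, that is 56 therapist slots.
- Boston enrols 112, so 16 groups and 32 slots. The Resources section lists 14 + 6 = 20 staff psychologists there.
- Therapists are trained once, at project start (D.3). The training is recorded in case a staff member joins later (D.6).
- D.3 spreads recruitment over seven waves in Years 1 to 4, so groups largely follow one another and the same pair could lead successive groups.

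**Effect of reuse on the test.** Inputs: 14 groups of 7 per arm; group ICC .07 (the pilot CAPS value in the power section); therapist-pair ICC r, assumed; k = number of groups led by each pair. A t-test on group means (26 df), ignoring pairs, stands in for the planned group-level model.

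- Group-mean variance excluding the pair component: s² = .07 + (1 − .07 − r)/7.
- True variance of the arm difference: 2 × [s²/14 + r × Σk²/14²].
- Variance that the group-only test estimates on average: (2/14) × [s² + r × (1 − Σk(k−1)/(14 × 13))].

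Example: two pairs per arm leading 7 groups each, r = .01.
- s² = .07 + .92/7 = .2014.
- True variance = 2 × [.01439 + .01 × 98/196] = .0388, so SE .197.
- Estimated variance = (2/14) × [.2014 + .01 × (1 − 84/182)] = .0295, so SE .172.
- Ratio .197/.172 = 1.15. The critical value 2.056 acts like 2.056/1.15 = 1.79 on 26 df, a two-sided error of about 8.4%.

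Type I error from 200,000 simulated null trials per cell, with the SE ratio from the formulas in brackets:

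| Pairs per arm (groups led) | r = .01 | r = .03 | r = .05 (bound) |
|---|---|---|---|
| 2 (7, 7) | 8.4% (1.15) | 15.1% (1.38) | 20.4% (1.57) |
| 4 (4, 4, 3, 3) | 6.5% (1.06) | 9.2% (1.17) | 11.7% (1.26) |
| 7 (2 each) | 5.5% (1.03) | 6.6% (1.07) | 7.4% (1.11) |
| 14 (1 each) | 5.0% (1.00) | 4.9% (1.00) | 5.1% (1.00) |

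Unequal loads of 8 and 6 groups, matching the site sizes, give practically the same results as 7 and 7. Placing the therapist component inside the planned ICC of .11 instead of adding it to .07 gives about 8%, 11% and 21% at r = .01, .02 and .05 for one pair per site per condition. The result does not depend on that choice.

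**The case against.** The nesting is openly argued and is a legitimate choice. Manuals, weekly supervision, matching, and independent adherence and competence ratings of 20% of sessions all reduce therapist variation. These safeguards stand and belong in the revised text, but they do not support the word *ensure*.

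A reader might go further than the documents allow in four ways.

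- **That the plan has therapists leading several groups.** It does not say so. Section D.2, to which D.3 refers, is not in the text available, and the Boston staff list is not a cap on who may serve. Reuse is strongly implied, not stated. With a separate pair for every group, the group level absorbs therapist variance and the standard-error point falls away.
- **That the whole error excess of a maximum-likelihood z-test is due to therapists.** Such a test sits near 7% here with no therapist variance at all, because there are only 28 groups. The t-test figures isolate the therapist part.
- **That a therapist ICC of .05 is a typical value.** It equals the entire group-level CAPS ICC reported for the earlier veteran group trial, which already contains therapist variance. It is a bound.
- **That the assessor-bias remark explains why therapists were left out.** The power section and D.7.a both also attribute clustering to treatment in groups. The remark conflicts with them, but it does not show why the therapist level is missing.

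**Conclusion.** The point stands and is worth correcting, though it does not undermine the design. The assurance in D.3 is not true of a trial in which therapists are nested within condition, and that conclusion needs no assumption.

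The standard-error point is conditional. It requires pairs to lead more than one group, and its size depends on a number of pairs and a therapist ICC that the documents do not give. Over a therapist ICC of .01 to .03, the effect runs from negligible with seven pairs per arm to a doubling or tripling of the nominal 5% with two.

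Nothing here shows that a difference between GCBT and SGP would be due to therapists. It shows only that the plan could not exclude it.

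**What to change.** Keep the nesting, and change the following.

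1. In D.3, replace the assurance with a statement that matching, manuals, supervision and fidelity ratings reduce therapist effects but cannot exclude them, and that they are confounded with condition.
2. Record both therapist IDs for every group, and report how many groups each therapist leads. This comes first, because stable pairs are not guaranteed and the choice in step 3 depends on it.
3. Pre-specify a sensitivity analysis reported beside the primary result. If there are enough pairs, add a therapist or pair random level with small-sample degrees of freedom. If not, recompute the primary confidence interval at therapist ICC 0, .01, .03 and .05 (labelled as a bound), using the actual number of groups per therapist. With two pairs per arm the pair level has only 4 − 2 = 2 degrees of freedom, so the ICC-range version must then carry the analysis.
4. In the power section, amend the statement that there is one clustered variable. Reconcile the assessor-bias sentence with the attribution of clustering to group treatment in the same section and in D.7.a.

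The cost is some wording, two ID fields per group and one extra analysis. Sample size and treatment delivery do not change. The downside is a wider interval in the sensitivity analysis and a more guarded conclusion.

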#### **D. 4. Measures**

The hypotheses state that relative to participants who are assigned to the *SGP* condition, participants who receive GCBT will show greater reductions in PTSD symptoms, report less utilization of health-care resources, and report less distress and impairment, at post-treatment

and 3 and 6 month follow-up assessments. Additionally, for patients with co-morbid Major Depressive Disorder (MDD), Generalized Anxiety Disorder (GAD), and/or Alcohol abuse prior to treatment, GCBT will produce significantly larger symptom reductions for these conditions, relative to *SGP* at post-treatment assessment and 3- and 6- month follow up. As well, gains in PTSD symptoms, distress and impairment will be maintained in the GCBT group at 12-month follow-up.

Measures selected to evaluate these hypotheses are described in the next section (see also Table 4).

### **Outcome variables:**

**Measures of PTSD symptoms** will include the Clinician Administered PTSD Scale - 5 (CAPS -5) and the Posttraumatic Check List - 5 (PCL-S-5). The CAPS-5 has been discussed in Section D1 (Study Participants). The CAPS-5 will serve as the primary outcome measure for PTSD. Both measures derived from the CAPS-5 will be used (presence/absence of PTSD diagnosis and overall PTSD severity score

Other measures include:

- The PTSD Checklist-5 (PCL-5; Weathers, Litz, Huska, & Keane, 1994) is self-report measure of PTSD, that corresponds to the DSM-5 symptoms of PTSD. Like the CAPS, the PCL can be scored to yield an overall severity score (total score). Psychometric properties of the prior PCL are sound (Weathers et al., 1994). The proposed project will use the PCL-S-5, a version that requests individuals to state the index event for which they are rating symptoms. In addition to the assessment map provided in Table 4, the PCL5 will be administered weekly during treatment, in order to track participant risk. Greater details about how the PCL data will be used to assure participant safety can be found in Section E.2.

**Measures of distress and impairment** Three subscales of the Medical Outcomes Study Short-Form Health Survey (SF-36; Ware & Sherbourne, 1992) will be used to index objective role functioning/impairment. These scales are the Role Limitations due to Physical Problems (role-physical), Role Limitations due to Emotional Problems (role-emotional), and Social Functioning subscales which appear to be minimally confounded with psychopathology. All three of these subscales have shown factorial validity and discriminative validity (Ware & Sherbourne, 1992).

- **Health care utilization** will be examined as an exploratory aim to investigate the effect of PTSD group treatment on health care utilization. This measure will be evaluated via record tracking. Veterans may obtain medical care within or outside of the VA system. When men initially enroll in the project, we will ask the names of their medical providers. Physician records in the VA system can be electronically accessed using the CPRS system. For physicians outside of the VA system, we will seek a signed release of information, which will permit contact to track the number of visits. The Project Coordinator will keep monthly records of the number of medical visits (excluding wellness visits) for each participant.

**Measures of comorbid anxiety, depression, and alcohol abuse** will include the *Structured Clinical Interview for DSM-IV* (SCID, Spitzer, et al. 1994), the *[name] Anxiety Inventory*, the *[name] Depression Inventory – II*, and an amended version of the *Short Inventory of Problems*. The SCID has been discussed in Section D1 (Study Participants). Both measures derived from the SCID (presence/absence of each additional disorder and global Clinical Severity Rating for each disorder) will be used. The SCID will not be administered at mid-treatment assessment. Other measures are:

- The [name] Anxiety Inventory (BAI; [name] et al., 1988) will be administered as a continuous measure of anxiety. The BAI is a 21-item scale that assesses anxiety and is believed to avoid confounding anxiety with depression. The BAI has established psychometric properties ([name] & Steer, 1991).
- The [name] Depression Inventory-II (BDI-II; [name] et al., 1996) will be administered as a continuous measure of depression. This 21-item questionnaire evaluates current depressive symptoms and has well-established reliability and validity ([name] et al., 1996).
- An amended version of the Drinkers Inventory of Consequences, named the Short Index of Problems (SIP; Miller et al., 1995) will be used to assess alcohol use and alcohol-related consequences. The SIP is a 15-item scale that includes five subscales: physical consequences, intrapersonal consequences, social responsibility consequences, interpersonal consequences, and impulse control consequences. The SIP possesses satisfactory psychometric properties (i.e., good internal consistency, good concurrent validity, good test retest reliability; (Forcehimes et al., 2007). The SIP will be supplemented with three questions that will assess how many days in the past 2 weeks the individual consumed alcohol, on average how many standard drinks were consumed on those days when he drank alcohol, and the number of days in the past 2 weeks on which 5 or more standard drinks were consumed. This assessment strategy was constructed in consultation with [name], Research Institute for the Addictions, Buffalo, NY. We have included a mid-treatment assessment period in our design; however, in order to reduce participant-burden we will not conduct the SCID diagnostic interview at the mid-treatment assessment time period.

The *Trauma Life Experience Questionnaire* self-report will be completed at baseline to obtain information on overall trauma exposure of the participants and will be used to identify the index event that will be referred to when completing CAPS-5 assessment.

The *Cognitive Emotion Regulation Questionnaire* is a brief, self-report measure of cognitive emotion regulation strategies. This measure will be completed to examine whether emotion regulation moderates or mediates treatment outcome. This measure will be administered every other week during treatment and at every assessment session.

**Treatment Process Measures** will be included as secondary measures. These four measures will be used in an exploratory fashion, to generate hypotheses about the impact of therapeutic process on outcome. These measures also will augment the ratings of therapist competence, by providing direct information about the group treatment experience from the group members themselves. The process measures will include:

- number of sessions attended;
- a widely-used measure of treatment credibility (Borkovec & Nau, 1972) to be administered at the conclusion of Session 1 (after the treatment rationale and specific procedures are explained). This measure asks patients to rate on a 10-point scale how logical

the treatment seems, their confidence in undergoing the treatment and recommending it to others, and their expectations for the treatment's success;

- The Client Satisfaction Questionnaire (Larsen, et al., 1979), a measure of participant satisfaction with treatment, will be administered at the last session of treatment. This 8-item measure assesses patients' satisfaction with treatment and has demonstrated concurrent validity;
- The California Group Psychotherapy Alliance Scales (CALPAS-P; Gaston, 1991), a measure of therapeutic alliance, will be administered. The 24 items of the CALPAS load on 4 subscales: Patient working capacity, Patient commitment, Working strategy consensus, and Therapist understanding and involvement. The CALPAS (Patient version) shows good psychometric properties. This measure will be administered every other treatment session in order to evaluate patients' perceptions of the group and examine whether alliance serves as a mediator of treatment outcome;
- To assess homework compliance, we will use the homework compliance form; for GCBT, this form was developed during the treatment development project. For SGP, a parallel form will be created. Therapists will rate the percentage of each homework assignment that each participant completes each week and provide a rating of homework quality, following Primakoff et al. (1986) and successfully used in other RCTs (e.g., Leung & Heimberg, 1996).
- To qualitatively measure participants' experiences of the two different kinds of group formats, 7 open-ended questions about their experience will be asked at the 1-month post-treatment assessment. Answers to these questions will supplement quantitative data. Responding to these questions will take 3-5 minutes, and answers will be written, not recorded.

**D.5. Follow-up:** In designing this RCT, it was important to demonstrate durability of changes following GCBT and SGP and so, included a follow-up interval. The patients will be assessed three times during a 1-year follow up interval (at 3-, 6-, and 12 months).

**D. 6. Between-site coordination:** We (Drs. [name], [name], and [name]) have worked effectively together over the past several years. Based on our collaborative work experience, we anticipate that our collaboration during the execution of the project will likewise be productive. We have collaboratively revised the GCBT treatment manual to be suitable for Veterans, organized the assessment battery to be used during pilot testing, and collected pilot data with two separate treatment groups. This section will delineate roles, including efforts designed to facilitate coordination between the PI's and the Co-I. In the initial months of the project, Drs. [name], [name] and [name] will write a procedures/operations manual. This manual will provide a detailed outline of each procedure, including recruitment procedures, each step in the assessment process, case management before and after treatment, specific procedures involved in treatment, and data management. The standardization of these procedures will ensure between-site coordination, as all personnel will have available a written set of directions to follow.

Importantly, all assessors and therapists will be trained at a common workshop. During the start-up phase of the project, an Assessment training workshop will be scheduled, led by [name]. This workshop will focus on administration of the CAPS and the SCID, with particular attention to differential diagnosis and use of the 0-8 clinical severity rating. A therapy training workshop will be scheduled simultaneously, to train the study therapists. [name] will coordinate the scheduling of these workshops. [name] will take responsibility for training

therapists in the SGP (present centered group treatment) protocol, and [name] will assume responsibility for training therapists in the GCBT protocol. These trainings will be digitally recorded so that they will be accessible throughout the project, which will allow consistency in training in the event that a staff member joins the project mid-way. Because the individuals who will fill these roles will have experience working with PTSD patients within a VA system, the two day training workshop will be conducted at an intermediate to advanced level.

Drs. [name] and [name] will be responsible for the day-to-day operations at the Boston and Providence sites, respectively. In particular, Drs. [name] and [name] will supervise recruitment of potential participants, and they will work closely with their project coordinators to ensure smooth operations of the proposed procedures. Drs. [name] and [name] will also assist with case management during the interval prior to randomization to a treatment condition, as well as during the follow-up interval. [name] will also maintain close contact with the project statistician, [name]. [name] will provide weekly supervision to therapists conducting GCBT and [name] will provide weekly supervision to therapists conducting the SGP treatment. Drs. [name], [name] and [name] will hold weekly conference calls for project planning and coordination, which will include discussion of recruitment efforts, issues that arise in case management, diagnostic reliability, and treatment fidelity.

**Is this RCT adequately statistically powered?** In the study design, several factors were involved in determination of sample size. **First**, we drew estimated effect sizes from the **two** pilot studies on GCBT and from a recent meta-analysis (Bradley et al., 2005). Within the MVA pilot study, which contrasted GCBT with a minimal contact comparison condition, effect sizes for PTSD measures ranged from .83 to 1.04 (Hedges's unbiased  $g$ , Hedges, 1981). Within our Vietnam veteran pilot data, the pre-post treatment effect size for the PCL-M was  $d = 1.43$ . Consulting the larger literature, Bradley et al. (2005) computed average effect sizes (Cohen's  $d$ ) of .84 for contrasts between CBT versus supportive therapy conditions and 1.01 for contrasts between ET + cognitive therapy versus supportive therapy conditions. However, in RCTs involving veterans, effect sizes tend to be smaller, owing to the chronicity and severity of combat-related PTSD in this population. In computation of sample size for this trial, we have selected a relatively low value of  $d$  (.50); review of available studies (including our own pilot data) suggests effect sizes ranging from 0.84 to 1.43. Recognizing that effect sizes for contrasts between CBT and supportive psychotherapy tend to average  $d = .84$  (Bradley et al., 2005), that data from samples with chronic PTSD tend to have smaller effects, relative to less severe samples, and that effect sizes drawn from relatively small samples can be unstable, we took a conservative stance in estimating the effect size for the GCBT versus SGP contrast to arrive at  $d = .50$ . **Second**, because treatment within both conditions of this RCT will occur in groups, the analytic plan must account for the cluster effect owing to the correlation of outcomes within groups (expressed as  $\rho$ , the intraclass correlation coefficient). There is one clustered variable in this design (individuals within groups) which will be adjusted for in determining sample size. Following guidelines provided by Hsieh (1988) and Diggle et al. (2002), we used an inflation factor that was driven by the  $\rho$  values from the MVA-related PTSD pilot data. In particular, the  $\rho$  estimate of 0.11 is a conservative assumption, based on the largest value obtained in the pilot MVA study. In the pilot MVA study ([name] et al., 2009), the  $\rho$  for the CAPS was 0.07, the  $\rho$  for the BDI-II was 0.03, and for the BAI, the  $\rho$  was 0.08. Within the Collaborative 420 study (Schnurr

et al., 2003), the  $\rho$  for the CAPS was 0.05. Thus, use of  $\rho = 0.11$  in our power calculations is a conservative assumption. Larger values of the  $\rho$  can occur when the outcome measures (among patients) have a concrete connection to one another. In studies of physician behavior within a clinic, the  $\rho$  values are larger when the physician directly contributes to the assessment of the patient outcome measures. For example, Stedman et al. (2008) analyzed two such studies, one study of patients within selected clinics who were followed to determine if their clinic physician did or did not provide osteoporosis management, and a second study of patients within clinics to determine if physician education induced physicians to improve the quality of osteoporosis management. In each study the  $\rho = 0.12$ . The outcome measure for the patient was the level of disease management delivered by the physician, an outcome directly determined by the physician. In contrast, for our proposed study, the person who assesses patient outcomes should have little or no effect on the values of the patient measure outcome. In our study, the  $\rho$  captures a subtler effect, namely, potential assessor bias, a much smaller effect than the effect of physician practice patterns. With a proposed group size of 7, a maximum  $\rho$  of 0.11, and  $d = 0.50$ , we estimated a total  $n$  of 196, using  $p < .05$ . Although only two of 14 outcome variables in the pilot study exceeded  $\rho > .10$  (see [name] et al., 2009), we felt it was preferable to be conservative regarding  $\rho$  levels in our power computations. **Third**, in computation of sample size, we relied on .80 power level, as is customary in power calculations for RCTs. Using these parameters, the total desired  $n$  will be 196 ( $n = 98$  per condition); each treatment group will begin with 7 men. Thus, based on previous studies on Group CBT, as well as current data regarding ICC in the context of clinical trials, we have been appropriately conservative in our power calculations.

In addition to statistical significance, we were concerned about the potential clinical significance of these data. Presently, there is no agreed-upon effect size that is thought to be clinically significant. This is difficult to determine because effect sizes hinge on many variables (e.g., the size and nature of the sample, the amount of variance in the assessment strategy, the amount of variance in treatment administration). In our power calculations, we have relied on a .80 power level, to have a sufficient sample size for this RCT for statistical significance. Unfortunately, there is no consensus in the treatment literature regarding what constitutes a clinically significant effect size; Friedman and colleagues (2006) suggest that clinically meaningful differences between 2 active treatments would be illustrated by an effect equal to or greater than .30 (Cohen's  $d$ ). Consultation with [name] (Project Statistician) thus indicates that the proposed  $n$  will be sufficient to determine whether GCBT produces clinically meaningful outcomes.

**Analytic approach:** Data from both sites will be combined prior to analyses. [name], the Project Statistician, will work in close collaboration with [name] to perform the analyses. Prior to testing hypotheses, the outcome data will be examined to assess if they meet the assumptions for the proposed statistics (Tabachnick & Fidell, 2001). If the assumptions are not met (e.g., the data depart from normality, multivariate outliers are present), appropriate data transformations will be used. Additionally, the GCBT and SGP groups will be examined for pre-treatment differences, to test for group equivalency. These analyses will involve a series of independent  $t$ -tests on each of the outcome measures as well as demographic variables. Pre-treatment differences between conditions will be incorporated into the models used to examine the primary hypotheses, as described below.

In any RCT, missing data are inevitable. Analysis of only complete cases is biased; likewise, values not missing at random can bias the results. Thus, analyses that impute missing data must accordingly increase standard errors. In designing this trial, we have included features that are intended to minimize attrition, such as the presence of a project coordinator (who will make regular contact with each patient before and after treatment). Even with these features, we expect some missing data. The analytic plan is designed to make maximum use of the data. In particular, we will use multilevel latent growth modeling (estimator = maximum likelihood [ML]) using Mplus software. Within this approach, missing data are handled with direct ML (cf. Allison, 2001), retaining an effective  $N = 196$  for all analyses. In addition to fostering statistical power, modern missing data methods such as direct ML (and multiple imputation) provide accurate parameter estimates and standard errors (assuming that values are missing at random), unlike traditional methods such as restricting analyses to completers only or intent-to-treat (ITT) analyses. If we suspect that values are not missing at random, we will turn to methods discussed by Molenberghs and Kenward (2007), that are likelihood-based, intended for ITT studies, and tractable enough for standard statistical programs such as SAS. Potential bias due to attrition will be assessed by modeling 'missingness' patterns. In effect, these methods increase standard errors of the crucial study estimates thereby accounting for this source of uncertainty. If attrition occurs in a random manner (missing at random implies 'missingness' may depend on covariates but not on previous values of the outcome measure) then the mixed model produces unbiased estimates and conservative standard errors. Evaluations of potential bias, when attrition is not missing-at-random, requires cutting-edge statistical methodology (Daniels & Hogan, 2008). We will perform sensitivity analysis under various not-missing-at random assumptions following Daniels and Hogan's (2008) methodology.

The study analyses will include all cases that were randomized into the trial, including individuals who dropped out of treatment. Thus, the distinction between ITT and completer analyses becomes artificial. Greater detail about the proposed analytic approach is discussed in the next section. We intend to contact participants who voluntarily drop out of treatment during what would have been their mid, post- and follow-up assessments, in order to provide as complete a data set (and effect size estimates) as possible.

